## 5.0 TREATMENT PLAN

5.1. All patients must be registered with Data Management at [name]. They will be interviewed first by the Research Nurse before registration.

5.1.1 Follicular lymphoma patients who are known not to have bcl-2 gene rearrangement will not be randomized -- they will proceed directly to therapy with the ATT regimen (see Appendix B).

If there is no threatening disease and the clinician judges that it is safe to wait for the bcl-2 data, the initiation of therapy may be delayed (This is encouraged.)

However, if therapy is needed, it will not be delayed just for the bcl-2 report. If bcl-2 status is not known or pending, patients will be randomized. If, after therapy with FND begins, a patient is found to be germline for bcl-2, the patient will be crossed over to ATT (see strategy outline in Appendix B).

5.1.2 Randomization will be stratified for: tumor mass size < 5 cm vs. ≥ 5 cm; age < 60; FLC histology; SL histology; and suitability for the watch-and-wait policy followed at other institutions.

5.2 ARM 1 (delayed anti-CD20 arm) will consist of consecutive courses of Fludarabine/Mitoxantrone/Dexamethasone (FND), followed by rituximab.

Agent	Dose	Days	Route	Time	Total Dose
Fludarabine	25 mg/m 	1-3	IV	15 min	75 mg/m 
Mitoxantrone	10 mg/m 	1	IV	15 min	10 mg/m 
Decadron	20 mg	1-5	IV or PO	15 min	100 mg

5.2.1 Duration of therapy and intervals between courses:

- a) The courses should be repeated every 28 days according to recovery from myelosuppression.
- b) The total length of treatment will be 8 courses unless cumulative myelosuppression is encountered, in which case the treatment will be finished after 6 courses. Cumulative myelosuppression is defined as recovery of granulocytes to ≥ 1,000 or platelets to >100,000 requiring more than 6 weeks.

5.2.2 Patients older than 60 years will receive full doses of chemotherapy. Anyone experiencing delayed recovery of granulocyte counts (>35 days) or neutropenic fever will be candidates for G-CSF (Neupogen), with the chemotherapy doses adjusted down one dose level. The G-CSF dose will consist of 300 mcg total dose daily, subcutaneously. The dose can be increased to 480 mcg daily at the clinician's discretion.

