## 5.6 Dose Modification Guidelines

### 5.6.1 Recommended Guidelines for Hematological Toxicity

Lowest granulocyte	Lowest platelet	Modification
> 1000 and	>100,000	Increase one level
>200 but <1000 or <200 for ≥ days	>20,000 but <100,000	No change
<200 for > 5 days and/or	<20,000	Decrease one level
Documented infection with neutropenia	Mucosal bleeding	Decrease one level

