### 5.6.2 For All Other Toxicities (see Appendix D)

Grade 0-2	No Change
3	Decrease one level
4	Stop Treatment

5.6.3 All courses will be held pending hematologic recovery to granulocytes >1,000 and platelets >100,000, and non-hematologic toxicities to grade <1.

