Alkaline phosphatase	WNL	> ULN - 2.5 x ULN	> 2.5 - 5.0 x ULN	> 5.0 - 20.0 x ULN	> 20.0 x ULN
Bilirubin	WNL	> ULN - 1.5 x ULN	> 1.5 - 3.0 x ULN	> 3.0 - 10.0 x ULN	> 10.0 x ULN
Bilirubin- graft versus host disease (GVHD)					
Note: The following criteria are used only for bilirubin associated with graft versus host disease.					
	normal	≥2 - <3 mg/100 ml	≥3 - <6 mg/100 ml	≥6 - <15 mg/100 ml	≥15 mg/100 ml
GGT (γ - Glutamyl transpeptidase)	WNL	> ULN - 2.5 x ULN	> 2.5 - 5.0 x ULN	> 5.0 - 20.0 x ULN	> 20.0 x ULN
Hepatic enlargement	absent	-	-	present	-
Note: Grade Hepatic enlargement only for changes related to VOD or other treatment related toxicity.					
Hypoalbuminemia	WNL	<LLN - 3 g/dl	≥2 - <3 g/dl	<2 g/dl	-

Toxicity	Grade				
	0	1	2	3	4
Liver dysfunction/failure (clinical) Note: Documented viral hepatitis is graded in the INFECTION category.	normal	-	-	asterixis	encephalopathy or coma
Portal vein flow	normal	-	decreased portal vein flow	reversal/retrograde portal vein flow	-
SGOT (AST) (serum glutamic oxaloacetic transaminase)	WNL	> ULN - 2.5 x ULN	> 2.5 - 5.0 x ULN	> 5.0 - 20.0 x ULN	> 20.0 x ULN
SGPT (ALT) (serum glutamic pyruvic transaminase)	WNL	> ULN - 2.5 x ULN	> 2.5 - 5.0 x ULN	> 5.0 - 20.0 x ULN	> 20.0 x ULN
Hepatic-Other (Specify, _____)	none	mild	moderate	severe	life-threatening or disabling
INFECTION/FEBRILE NEUTROPENIA					
Catheter-related infection	none	mild, no active treatment	moderate, localized infection, requiring local or oral treatment	severe, systemic infection, requiring IV antibiotic or antifungal treatment or hospitalization	life-threatening sepsis (e.g., septic shock)
Febrile neutropenia (fever of unknown origin without clinically or microbiologically documented infection) (ANC < 1.0 x 10  /L, fever ≥38.5°C) Note: Hypothermia instead of fever may be associated with neutropenia and is graded here.	none	-	-	Present	Life-threatening sepsis (e.g., septic shock)
Infection (documented clinically or microbiologically) with grade 3 or 4 neutropenia (ANC < 1.0 x 10  /L) Note: Hypothermia instead of fever may be associated with neutropenia and is graded here. In the absence of documented infection with grade 3 or 4 neutropenia, grade as Febrile neutropenia.	none	-	-	present	life-threatening sepsis (e.g., septic shock)
Infection with unknown ANC Note: This toxicity criterion is used in the rare case when ANC is unknown.	none	-	-	present	life-threatening sepsis (e.g., septic shock)

Toxicity	Grade				

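### After neutropenic fever without documented infection, section 5.2.2 lowers FND by one dose level, but the 5.6.1 dose table can leave the dose unchanged and does not refer to 5.2.2

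*Combined protocol and SAP*

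**What the plan says.** Four places in the protocol bear on the dose after a febrile neutropenic episode.

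- **Section 5.2.2** (FND; Arm 2 is referred to it by 5.3). Anyone with granulocyte recovery taking more than 35 days or "neutropenic fever will be candidates for G-CSF (Neupogen), with the chemotherapy doses adjusted down one dose level". No nadir, grade or documentation of infection is required.
- **Section 5.6.1** (dose table for hematological toxicity). A granulocyte nadir of ">200 but <1000", with platelets above 20,000 but below 100,000, leads to no change. One level down requires granulocytes below 200 for more than 5 days, platelets below 20,000, mucosal bleeding, or "Documented infection with neutropenia".
- **Sections 5.6.2 and 5.6.3.** All other toxicities are handled by Appendix D grade: one level down at grade 3, "Stop Treatment" at grade 4. Section 5.6.3 adds: "All courses will be held pending hematologic recovery to granulocytes >1,000 and platelets >100,000".
- **Appendix D.** Febrile neutropenia is defined as "fever of unknown origin without clinically or microbiologically documented infection", with granulocytes below 1,000. It is listed under infection, separately from documented infection and outside the blood and bone marrow category. Grade 3 is the event being present; grade 4 is life-threatening sepsis.

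**The concern.** Section 5.6 carries the title of the dose modification guidelines, and it is where a clinician would look for the next dose. Other parts of the protocol send readers there without mentioning 5.2.2: section 5.7.4 for interferon and Appendix B, part IV, for ATT. A clinician who uses only the table after a fever-only episode can repeat the same FND dose and will see nothing about G-CSF. That is contrary to 5.2.2, and it errs towards more treatment in a patient who has just had neutropenic fever. The other 5.2.2 trigger, recovery beyond 35 days, is also missing from the table. What is at stake is patient safety and consistent dosing under one protocol.

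**Working it through.** There is no figure in the plan to reproduce. The check is a side-by-side reading, followed by the dose arithmetic.

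**Step 1: which 5.6.1 line applies.** Take neutropenic fever with no documented infection, a granulocyte nadir of 200 to 1,000 and platelets of 20,000 to 100,000. The dose-increase line needs a nadir above 1,000, which the Appendix D definition rules out. None of the four triggers for one level down is met. Only the no-change line is left. The part of that line about shorter periods below 200 is incomplete in the text available and is not used here. If platelets are above 100,000, no line fits literally, so the claim is limited to the stated platelet range. With granulocytes below 200 for more than 5 days, or platelets below 20,000, the table and 5.2.2 agree.

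**Step 2: the rules side by side.**

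| Event without documented infection | 5.2.2 | 5.6.1, nadir as in step 1 | 5.6.2, if an other toxicity |
|---|---|---|---|
| Grade 3 (present) | one level down | no change | one level down |
| Grade 4 (life-threatening sepsis) | one level down | not relied on (see the objection) | stop |

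**Step 3: size of one level.** From 5.6.4, fludarabine is 25 mg/m2 at level 0 and 20 at level -1, each for three days; mitoxantrone is 10 and 8. Fludarabine per course is therefore 3 x 25 = 75 or 3 x 20 = 60 mg/m2, a 20% drop, and the mitoxantrone drop is also 20%. From 5.2.1(b), the number of courses N is 8, or 6 with cumulative myelosuppression. For an event in course k, starting at level 0 with no other dose change, the share of total fludarabine at issue is 15 x (N - k) / (75 x N).

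| Event in course | N = 8: no change / one level down | Share | N = 6: no change / one level down | Share |
|---|---|---|---|---|
| 1 | 600 / 75 + 7 x 60 = 495 | 17.5% | 450 / 75 + 5 x 60 = 375 | 16.7% |
| 4 | 600 / 300 + 4 x 60 = 540 | 10% | 450 / 300 + 2 x 60 = 420 | 6.7% |
| last | 600 / 600 | 0% | 450 / 450 | 0% |

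**Step 4: grade 4.** After an event in course 1 of 8, one level down gives 495 mg/m2 in total and stopping gives 75. After an event in course 4 of 8, the totals are 540 and 300.

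**The case against.** The best reply is that the count lines in 5.6.1 are defaults, and a complication overrides them. A patient with a nadir of 500 and a documented infection meets both the no-change line and a decrease line, and the decrease plainly governs. Section 5.2.2 can be read as one more such trigger, and a specific rule supplementing a general table headed as recommended guidelines is an ordinary construction. At grade 3, 5.6.2 gives the same answer as 5.2.2. Much of this stands: the intended grade 3 rule is probably 5.2.2. What it does not answer is that the table lists its own complication triggers, names only documented infection among infections, and gives no sign that a further trigger sits elsewhere.

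Four stronger readings are tempting, and the documents do not support them.

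- **A three-way conflict at grade 4** (same dose, one level down, or stop). This mixes two classifications. If the event is hematological, the 5.6.2 stop does not arise; if it is an other toxicity, 5.6.2 governs and the nadir line does not. Repeating the full dose after life-threatening sepsis is not a realistic reading either, since 8.3 and 12.1 require immediate report to the Study Chairman. The live question is 5.2.2 against 5.6.2.
- **A gap for documented neutropenic infection.** There is none: 5.6.1 and 5.2.2 both give one level down.
- **Bias between arms or loss of power.** The same rules apply to both arms, and nothing here enters the sample size calculation.
- **A count of affected patients.** The documents give no rate of neutropenic fever, so any count would rest wholly on assumed rates.

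The hold in 5.6.3 and the reports to the Study Chairman are real safeguards, but none of them states the dose at which the next course starts.

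**Conclusion.** The inconsistency holds in a limited form. For neutropenic fever without documented infection, at a granulocyte nadir of 200 to 1,000 and platelets of 20,000 to 100,000, the table gives no change where 5.2.2 gives one level down with G-CSF candidacy. The recovery trigger is likewise absent from the table. The difference is 20% of each later course, hence 17.5% of total fludarabine at most and nothing after an event in the last course. This assumes a start at level 0 and no later re-escalation, which 5.6.1 would allow and which would narrow the gap. At grade 4 the choice between one level down and stopping is unresolved only if febrile neutropenia counts as an other toxicity; its place in Appendix D supports that reading but does not settle it. This is a patient-safety wording correction that should be made, not a flaw in the design or the analysis.

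**What to change.** 1. In 5.6.1, add to the lines for one level down: *FND courses: neutropenic fever without documented infection, or granulocyte recovery >35 days (see 5.2.2, including G-CSF); this prevails over the no-change line.* This carries an existing rule into the table. The restriction to FND is needed because 5.7.4 and Appendix B also send interferon and ATT readers to section 5.6.
2. In 5.6.2, add: *Grade 3 febrile neutropenia: see 5.2.2 and 5.6.1.* The sponsor should also state whether 5.2.2 or the stop rule applies to grade 4 febrile neutropenia without documented infection. That is a medical decision, and the review does not propose an answer.

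The rule for documented neutropenic infection should stay as it is. The cost is one added table line, one cross-reference and one sponsor decision, with no added visit, test or analysis.

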5.2.3 Rituximab Adjuvant Therapy

Starting at 12 months, after collection of the 12-month PCR samples (Sec 7.2), rituximab will be given monthly for 6 doses total.

The dose will be 375 mg/m^2 IV. Interferon maintenance will usually have commenced about 3-4 months before the rituximab doses start. When IFN and rituximab doses are given in the same month, the rituximab dose will be given first, with decadron permitted (but not mandatory) and the IFN will begin on day 2 of each cycle, or may be delayed for 1-2 days if needed (see 5.7.3).

When rituximab is given by itself (without IFN), decadron 8 mg IV or PO as a pre-medication is permitted but not mandatory (and see also 5.4).

5.3 ARM 2 (concurrent anti-CD20 arm) will consist of FND in conjunction with rituximab. Rituximab will be given on days 1 and 8 of course 1, then on day 1 only of courses 2-5, as outlined below:

- course 1:

rituximab 375 mg/m^2 d.1 & 8 IV  
(see section 5.4 for details of administration)  
fludarabine 25 mg/m^2 d. 2-4 IV  
mitoxantrone 10 mg/m^2 d.2 IV  
dexamethasone 20 mg d. 1-5 IV or PO  
(note dexamethasone starts a day earlier than in the usual FND schedule, so that the first dose of rituximab is given in conjunction with steroid)

- courses 2-5:

rituximab 375 mg/m^2 d.1 IV  
(see section 5.4 for details of administration)  
fludarabine 25 mg/m^2 d. 2-4 IV  
mitoxantrone 10 mg/m^2 d.2 IV  
dexamethasone 20 mg d. 1-5 IV or PO  
(note dexamethasone starts a day earlier than in the usual FND schedule, so that the first dose of rituximab is given in conjunction with steroid)

- courses 6 - 8:

same as for arm 1 (i.e., FND without concurrent rituximab) -- see Section 5.2, especially 5.2.1 and 5.2.2 concerning interval (q28 d), guidelines for use of G-CSF (applicable for all courses), and guidelines for omitting courses 7 & 8 if there is cumulative myelosuppression

#### 5.4 Details Pertaining to Rituximab Administration

##### 5.4.1 Rituximab Dose

All patients enrolled into the study will receive fixed doses of rituximab at 375 mg/m^2. In calculating body surface area, actual height and weight should be used, that is, there will be no downward adjustment to "ideal" weight. Dosage for all treatments will be calculated using the patient's body surface area as determined during the baseline evaluation. The dose level of rituximab will not be adjusted thereafter.

##### 5.4.2 Method of Administration

**CAUTION: DO NOT ADMINISTER AS AN INTRAVENOUS PUSH OR BOLUS.**

Rituximab infusions will be administered to patients in an outpatient clinic setting. To decrease the incidence of infusion-related adverse events, oral premedication (650 mg of acetaminophen and 25-50 mg diphenhydramine hydrochloride) may be administered prior to starting

each infusion of rituximab. Decadron 8 mg IV or PO is also permitted. A peripheral or central intravenous (IV) line will be established. During the rituximab infusion, the patient's vital signs (blood pressure, pulse, respiration, temperature) should be monitored every 15 minutes x 4 or until stable and then hourly until the infusion is discontinued.

Available at the bedside prior to rituximab administration will be:

- (a) epinephrine for subcutaneous injection;
- (b) diphenhydramine hydrochloride for intravenous injection; and
- (c) resuscitation equipment for the emergency management of anaphylactoid reactions.

The initial dose rate at the time of the first rituximab infusion should be 50 mg/hr for the first hour. If no toxicity is seen, the dose rate may be escalated gradually (50 mg/hr increments at 30-minute intervals) to a maximum of 400 mg/hr. If the first dose of rituximab is well tolerated, the starting flow rate for the administration of subsequent doses will be 100 mg/hour then increased gradually (100 mg/hr increments at 30-minute intervals) not to exceed 400 mg/hr.

Since transient hypotension has been reported during rituximab infusions, consideration should be given to withholding anti-hypertensive medications the day of the rituximab infusion. Patients may experience transient fever and rigors with rituximab. When these side effects are noted, the antibody infusion should be temporarily slowed or discontinued, the patient should be observed, and the severity of the side effects should be evaluated. The patient should be treated according to the best available local practices and procedures. Following observation, when the patient's symptoms improve, the infusion should be continued, initially at 1/2 the previous rate and gradually escalated to a maximum rate of 300 mg/hour (see table below). Following the antibody infusion, the IV line should be kept open for medications, as needed. If there are no complications, the IV line may be discontinued after one hour of observation. If complications occur during the rituximab infusion, the patient should be observed for two hours after the completion of the infusion.

**In patients with detectable circulating lymphoma cells, it is strongly advised that the initial rate of infusion be reduced to 25 mg/hr.** Patients with detectable circulating cells may experience more frequent and severe transient fever and rigors, shortness of breath, and hypotension with rituximab. When these side effects are noted, the antibody infusion should be temporarily slowed or discontinued, the patient should be observed, and the severity of the side effects should be evaluated. The patient should be treated according to the best available local practices and procedures. Following observation, when the patient's symptoms improve, the infusion should be continued, initially at 1/2 the previous rate and gradually escalated to a maximum rate of 300 mg/hour (see table below). Subsequent infusions may be carried out at a gradually increased infusion rate of up to 400 mg/hr maximum. If the first dose of rituximab

is well tolerated, the starting flow rate for the administration of subsequent doses will be 100 mg/hr then increased gradually.

Following the antibody infusion, the IV line should be kept open for medications, as needed. If there are no complications, the IV line may be discontinued after one hour of observation. If complications occur during the rituximab infusion, the patient should be observed for two hours after the completion of the infusion.

Dose Rate Decrease to 1/2	Fever > 38.5°C	or	Rigors Mild Moderate	or	Mucosal congestion/ Edema Mild Moderate	or	Drop in Systolic BP > 30 mm Hg
-------------------------------------	--------------------------	----	-----------------------------------	----	--	----	--

5.4.3 Adverse Clinical Events - see Appendix E

## 5.5 Prophylaxis for Pneumocystis Carinii

5.5.1 all patients will receive prophylaxis with trimethoprim-sulfa (TMP/SMX) as follows:

Two DS tablets twice weekly on Saturday and Sunday.

5.5.2 for TMP/SMX allergy, patients will receive pentamidine aerosol therapy: 300 mg q 4 weeks using a Respigard II nebulizer

5.5.3 for any problems, please consult PI and/or ID

## 5.6 Dose Modification Guidelines

### 5.6.1 Recommended Guidelines for Hematological Toxicity

Lowest granulocyte	Lowest platelet	Modification
> 1000 and	>100,000	Increase one level
>200 but <1000 or <200 for ≥ days	>20,000 but <100,000	No change
<200 for > 5 days and/or	<20,000	Decrease one level
Documented infection with neutropenia	Mucosal bleeding	Decrease one level

### 5.6.2 For All Other Toxicities (see Appendix D)

Grade 0-2	No Change
3	Decrease one level
4	Stop Treatment

5.6.3 All courses will be held pending hematologic recovery to granulocytes >1,000 and platelets >100,000, and non-hematologic toxicities to grade <1.

5.6.4 Dose levels for FND

Level	-2	-1	0	+1
Fludarabine (qd x 3)	16/m 	20/m 	25/m 	30/m 
Mitoxantrone (d.1)	6.4/m 	8/m 	10/m 	12/m 
Dexamethasone (qd x 5)	20 mg	20 mg	20 mg	20 mg

5.7 Interferon alfa-2b (Intron A) Maintenance

5.7.1 After completion of FND ± rituximab, patients will receive interferon alfa-2b (Intron A) maintenance.

5.7.2 Maintenance (for CR, PR, and "CRu" patients)

	day 1	2	3	4-14	
Dexamethasone (mg)	8	8	8	-	} Repeat q mo for 12 cycles
Interferon (x 10  u/m  )	3	3	3	3	

5.7.3 IFN maintenance schedule for these receiving rituximab adjuvant therapy on delayed anti-CD20 arm:.

The IFN will start 1 month after the final FND course. Usually this will be before 12 months, i.e., before rituximab maintenance for patients on the delayed anti-CD20 arm.

When IFN and rituximab are given in the same month, the schedule will be as follows (see also 5.2.3):

	day 1	2+	3	4-15
rituximab (mg/m  )	375	-	-	-
dexamethasone (mg)	8*	8	8	-
Interferon alfa (x 10  u/m  )	-	3	3	3

\* decadron pre-med is optional but encouraged

+ day 2 if possible, but delay of 1-2 days permitted between rituximab and IFN

5.7.4 Dose Modification Guidelines for Interferon

Level	-2	-1	0	+1
Interferon (x 10  u/m  )	1	2	3	5

Interferon guidelines for hematologic toxicity same as for chemotherapy (see 5.6.1). For non hematologic toxicity:

Grade

0-1	Increase 1 level if appropriate (escalation anticipated to be done infrequently )
2	No change
3	Decrease 1 level
4	Hold treatment; discuss with study chairman

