Mood alteration-anxiety agitation	normal	mild mood alteration not interfering with function	moderate mood alteration interfering with function, but not interfering with activities of daily living	severe mood alteration interfering with activities of daily living	suicidal ideation or danger to self
Mood alteration-depression	normal	mild mood alteration not interfering with function	moderate mood alteration interfering with function, but not interfering with activities of daily living	severe mood alteration interfering with activities of daily living	suicidal ideation or danger to self
Mood alteration-euphoria	normal	mild mood alteration not interfering with function	moderate mood alteration interfering with function, but not interfering with activities of daily living	severe mood alteration interfering with activities of daily living	danger to self
Neuropathic pain is graded in the PAIN category.					
Neuropathy- cranial	absent	-	present, not interfering with activities of daily living	present, interfering with activities of daily living	life-threatening, disabling

Toxicity	Grade				
	0	1	2	3	4
Neuropathy-motor	normal	subjective weakness but no objective findings	mild objective weakness interfering with function, but not interfering with activities of daily living	objective weakness interfering with activities of daily living	paralysis
Neuropathy-sensory	normal	loss of deep tendon reflexes or paresthesia (including tingling) but not interfering with function	objective sensory loss or paresthesia (including tingling), interfering with function, but not interfering with activities of daily living	sensory loss or paresthesia interfering with activities of daily living	permanent sensory loss that interferes with function
Nystagmus Also consider Vision-double vision.	absent	present	-	-	-
Personality/behavioral	normal	change, but not disruptive to patient or family	disruptive to patient or family	disruptive to patient and family; requiring mental health intervention	harmful to others or self; requiring hospitalization
Pyramidal tract dysfunction (e.g., ↑ tone, hyperreflexia, positive Babinski, ↓ fine motor coordination)	normal	asymptomatic with abnormality on physical examination	symptomatic or interfering with function but not interfering with activities of daily living	interfering with activities of daily living	bedridden or disabling; paralysis

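### The interferon dose table (5.7.4) writes no hold for new depression before grade 4; at grade 3 it lowers the dose and continues, and the protocol does not say whether the 5.6.3 recovery rule covers interferon cycles

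*Combined protocol and SAP*

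**What the plan says.** Interferon is given at 3 x 10^6 U/m2 daily for 14 days of each 28-day cycle, for 12 cycles (treatment plan, part III; 5.7.2). Section 5.7.4 lists dose levels of 1, 2, 3 and 5 x 10^6 U/m2 (levels -2 to +1). For blood counts it refers to the chemotherapy rule in 5.6.1. For all other toxicity it has its own table:

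- grade 0-1: "Increase 1 level if appropriate", with a note that this should be infrequent;
- grade 2: no change;
- grade 3: "Decrease 1 level";
- grade 4: "Hold treatment; discuss with study chairman".

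Toxicities are graded by Appendix D (8.3). There, grade 3 depression is "severe mood alteration interfering with activities of daily living" and grade 4 is "suicidal ideation or danger to self".

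For other toxicities, 5.6.2 makes no change at grades 0-2, reduces one level at grade 3 and says "Stop Treatment" at grade 4. Section 5.6.3 adds a recovery condition: "All courses will be held pending hematologic recovery to granulocytes >1,000 and platelets >100,000, and non-hematologic toxicities to grade <1". Section 5.7.4 states no recovery condition of its own and does not mention 5.6.3.

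Depression is flagged elsewhere. Section 4.4 gives a history of depression as a reason that may count against interferon, and it invites discussion of any interferon concern with the P.I. Appendix F, item 2, lists pre-existing psychiatric illness.

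**The concern.** The protocol recognizes depression as a problem with interferon, but its specific text concerns patients who bring a psychiatric history to the trial. A patient who becomes depressed during the 12 cycles falls under the general table in 5.7.4. If that table is followed as written, a patient with severe depression keeps receiving the drug at a lower dose, and the first written instruction to withhold it comes once there is suicidal thinking or danger to self. A patient with mild depression may even have the dose raised.

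The matter at stake is patient safety, not the error rates of the trial. Part of the exposure depends on whether 5.6.3 applies to interferon, so two investigators could follow the text in good faith and treat the same patient differently.

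**Working it through.** The plan states no figure to reproduce. The check sets the depression grades of Appendix D against the dose rules, then works out the doses involved.

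**Rules side by side, for depression that begins on interferon**

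| Grade (Appendix D) | Interferon table, 5.7.4 | Table in 5.6.2 |
|---|---|---|
| 1, mild | may rise one level | no change |
| 2, moderate | no change | no change |
| 3, severe | down one level | down one level |
| 4, suicidal thinking or danger | hold and discuss | stop |

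On when the drug is interrupted, the two tables differ only at grade 4. At grade 3 the action is the same. The other difference is the escalation allowed at grade 0-1.

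**Dose per 28-day cycle** (14 doses, in 10^6 U/m2)

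- Level 0: 14 x 3 = 42.
- Level -1, after grade 3: 14 x 2 = 28; (3 - 2)/3 = 33% lower. Under a hold it would be 0.
- Level -2, after a second grade 3 reduction: 14 x 1 = 14. No lower level is listed.
- Level +1, permitted at grade 1: 14 x 5 = 70; (5 - 3)/3 = 67% higher.

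**What 5.6.3 changes**

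- *If it covers interferon cycles*, the next cycle waits until depression is below grade 1. Only the current cycle is exposed. If grade 3 begins after the first dose, 14 - 1 = 13 doses remain. Section 5.7.4 does not say whether the reduction takes effect mid-cycle, so this is 13 x 2 = 26 to 13 x 3 = 39 x 10^6 U/m2.
- *If it does not*, nothing written delays the next cycle at grade 3, and further full cycles may be given at the reduced level.

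**Other text searched for a hold**

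- Section 12.1 requires reporting of life-threatening toxicity, and of unexpected and serious toxicity of grade 3 or 4. It is a reporting duty.
- Section 4.4 and the opening of Appendix F lead to a discussion with the P.I. They set no threshold for depression that begins on treatment.

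**The case against.** The strongest reply is that 5.6.3 already closes most of the gap. It speaks of all courses without limit and sits under the general dose-modification heading. Section 5.6.2 has the same form as 5.7.4: its grade 3 row lowers the dose and contains no hold, because 5.6.3 decides when the next course may start. Section 5.7.4 can be read in the same way. This stands as a possible reading, and the documents do not rule it out. They do not establish it either: 5.7.4 cites 5.6.1 alone, and interferon is scheduled in cycles. Even on this reading, 5.6.3 governs only the start of the next cycle. The remaining daily doses of the current one are not covered.

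A second reply is that judgment is available. Section 5.7.4 is titled as guidelines, escalation is qualified and expected to be rare, Appendix F also covers dose modification, and 4.4 is open to any concern. All of this is true. It makes escalation in a depressed patient unlikely, but it leaves continuing as the written default at grade 3.

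A third reply is that the documents give no basis for any particular threshold, and that interferon drug information is only available on request (3.1). This is fair. The grade 3 hold is a safety judgment. The recovery limit proposed below is the protocol's own.

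A reader might infer that the protocol treats depression on chemotherapy more strictly at grade 3. The tables do not support that: the action is identical, and the only further contrast would be 5.6.3, whose scope is the open question.

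**Conclusion.** The point holds for the table in 5.7.4. By itself that table continues interferon through severe depression at a dose one level lower, and it first writes a hold at grade 4. Per patient, the exposure is at most 13 further doses in the current cycle if 5.6.3 covers interferon. If it does not, further full cycles may follow, starting at 28 x 10^6 U/m2 each for a patient reduced from level 0. These figures assume the standard 14-dose cycle.

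A reader might conclude that the protocol as a whole withholds nothing until a patient is suicidal. That goes too far, because 5.6.3 may already delay the next cycle, and 4.4, Appendix F and 12.1 can each bring the case to the P.I. or Study Chairman. Nor do the documents show how many patients would be affected. This is a design choice that should be changed for safety. It is not a numerical error and does not threaten the primary comparison.

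**What to change.** Add to 5.7.4:

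> *For depression: do not escalate if any grade is present. At grade 3, hold interferon at once, including the rest of the current cycle, and discuss with the P.I. Resume one level lower only after recovery to the 5.6.3 limit (grade <1). Section 5.6.3 applies to interferon cycles for depression.*

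Leave the grade 4 row and Appendix F as they are.

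Costs:

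- Interferon is interrupted in some patients, probably few; the documents give no number. Planned doses are 12 x 14 = 168, so a cycle skipped rather than postponed is 14/168 = 8.3%.
- Because the 5.6.3 limit is below grade 1, a patient still at grade 1 or 2 when the next cycle is due would also wait. If the sponsor does not want that, the same paragraph should say so.
- Grading mood before each 28-day cycle may need a brief extra contact. Section 8.3 records toxicity before each course, but whether interferon cycles count as courses is the same open question. Section 11.1 requires the physician and nurse to see the patient only every 2-3 cycles, that is, every 56 to 84 days.
- The rule is the same in both arms. The sample size and the definition of the primary endpoint do not change.
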